6.8 Treatment exposure and compliance

Pharmacokinetic parameters (measures of treatment exposure) will be determined in all subjects treated with LNP023, as detailed in [Section 8.7](#).

The investigator must promote compliance by instructing the subject to take the study treatment exactly as prescribed and by stating that compliance is necessary for the subject's safety and the validity of the study. The subject must also be instructed to contact the investigator if he/she is unable for any reason to take the study treatment as prescribed.

Compliance will be assessed by the Investigator and/or study personnel at each visit using pill counts and information provided by the subject using a diary. This information should be captured in the source document at each visit. All study treatment dispensed and returned must be recorded in the Drug Accountability Log.

6.9 Recommended treatment of adverse events

At present, there is insufficient information to provide specific recommendations regarding treatment of AEs. There is no treatment that can reverse the activity of LNP023. LNP023 is a small molecule with a half-life of 12 hours. Potential AEs should therefore be treated symptomatically at the discretion of the Investigator. Medication used to treat AEs must be recorded on the concomitant medications/significant non-drug therapies CRF.

6.10 Rescue medication

Not applicable.

6.11 Concomitant treatment

The investigator must instruct the subject to notify the study site about any new medications he/she takes after the subject was enrolled into the study.

All prescription medications, over-the-counter drugs and significant non-drug therapies (including physical therapy and blood transfusions) administered or taken within the timeframe defined in the entry criteria prior to the start of the study and during the study, must be recorded in the appropriate CRF.

Prophylactic antibiotics (eg penicillin V or erythromycin) may be given at investigator's discretion.

Medication entries should be specific to trade name, the single dose and unit, the frequency and route of administration, the start and discontinuation date and the reason for therapy.

Each concomitant drug must be individually assessed against all exclusion criteria/prohibited medication (see [Section 5.2](#)). If in doubt, the investigator should contact Novartis before randomizing a subject or, if the subject is already enrolled, to determine if the subject should continue participation in the study.

7 Study completion and discontinuation

7.1 Study completion and post-study treatment

Each subject will be required to complete the study in its entirety and thereafter no further study treatment will be made available to them.

Study completion is defined as when the last subject completes their Study Completion visit (EOS), and any repeat assessments associated with this visit have been followed-up appropriately by the Investigator, or in the event of an early study termination decision, the date of that decision.

All randomized and/or treated subjects should have a safety follow-up visit 90 days after last administration of study treatment. The information collected is kept as source documentation. All SAEs reported during this time period must be reported as described in [Section 9.2](#) and the Site Operations Manual. Documentation of attempts to contact the subject should be recorded in the source documentation.

7.2 Discontinuation of study treatment

Discontinuation of study treatment for a subject occurs when study treatment is stopped earlier than the protocol planned duration. Discontinuation of study treatment can be decided by either the subject or the investigator.

Study treatment must be discontinued under the following circumstances:

- Subject decision - subjects may choose to discontinue study treatment for any reason at any time.
- The investigator believes that continuation would negatively impact the safety of the subject or the risk/benefit ratio of trial participation.
- Any protocol deviation that results in a significant risk to the subject's safety.
- Pregnancy (see [Section 8.6](#) (Safety) and [Section 9.6](#) (Pregnancy reporting))
- Use of prohibited treatment as outlined in [Table 5-1](#).
- Any laboratory abnormalities that in the judgment of the investigator, taking into consideration the subject's overall status, prevents the subject from continuing participation in the study
- Clinically symptomatic and suspected COVID-19 (+) and/or COVID-19 (+)

The appropriate personnel from the site and Novartis will assess whether investigational drug treatment should be discontinued for any subject whose treatment code has been broken inadvertently for any reason.

If discontinuation of study treatment occurs, investigator must determine the primary reason for the subject's premature discontinuation of study treatment and record this information on the appropriate CRF.

Subjects who discontinue study treatment or who decide they do not wish to participate in the study further should NOT be considered withdrawn from the study UNLESS they withdraw their consent (see [Section 7.3](#), Withdraw of Informed Consent). Where possible, they should return for EOS visit within 14 days after last study medication administration. If they fail to

return for EOS visit for unknown reasons, every effort (e.g. telephone, e-mail, letter) should be made to contact the subject/pre-designated contact as specified in [Section 7.4](#). (Lost to follow-up). This contact should preferably be done according to the study visit schedule.

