- T3, T4, TSH, reversed T3, FSH, LH, testosterone and DHT
- Vital signs
- 12-lead ECG (PR interval, QRS duration, heart rate, RR, QT, QTcF)
- AEs

Efficacy (proteinuria; renal function), PK, [REDACTED] will also be conducted through the study.

[figure not shown]
Patients should return to the site on a regular basis for follow up assessments and approximately 90 days after last dosing for study completion evaluations (EOS).

Design of Part 1:

Approximately forty-eight patients will be enrolled in Part 1 to allow for 40 patients to complete this part of the study. These patients will be randomized to treatment groups as follows: 14 to placebo, 10 to LNP023 10 mg, 10 to LNP023 50 mg and 14 to LNP023 200 mg, all b.i.d.

Study duration for patients enrolled in Part 1 will be of approx. 270 days.

Figure 3-1 Part 1

Design of Part 2:

An interim analysis will be performed when approximately 48 patients have been randomized in Part 1 and have completed treatment to Day 90 (or withdrawn from the trial), as described in the interim analysis section ([Section 3.5](#)).

The design and doses tested for Part 2 will be determined according to pre-specified rules that will be defined in full in the Data Monitoring Committee (DMC) charter. First, a sample size re-estimation will be performed to determine the number of patients to be randomized in Part 2 and secondly, a decision will be made on which dose (either 25 mg or 100 mg b.i.d) is to be added in Part 2. The sample size for Part 2 will be chosen to be in the range of 48 to 100 patients (i.e. to aim for 40 – 85 patients completing the 90 day treatment period in Part 2 of the study). Patients who are enrolled in Part 2, either in screening or run-in phase will not receive blinded study treatment until the interim analysis on Part 1 is completed and DMC recommends to proceed to Part 2 of the study. As a result of available data from interim analysis Part 1 (IA1) of the trial, part 2 of the study will recruit approximately 50 randomized patients.

[figure not shown]
The selection of doses to be used in Part 2 will be guided by the results seen in Part 1. Two scenarios will be considered:

1. placebo, 10 mg, 50 mg, 100 mg and 200 mg b.i.d.
2. placebo, 10 mg, 25 mg, 50 mg and 200 mg b.i.d.

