¹⁴ Serum pregnancy test required at screening, urine pregnancy test at further time points

¹⁵ For Part 1, Day 90 (Visit 160) is End of Treatment (EOT) and Day 180 (Visit 1999) is End of Study (EOS); for Part 2, Day 180 (Visit 180) is End of Treatment (EOT) and Day 270 (Visit 2999) is End of Study (EOS).

¹⁶ To be collected pre-dose.

¹⁷ Total Cholesterol, LDL, HDL, Triglycerides, Glucose under fasting condition will be measured at baseline (Visit 20), EOT (Visit 160) in Part 1, Visit 160 and EOT (Visit 180) in Part 2.

¹⁸. At screening UPCR can be measured from first morning void OR 24h urine collection.

¹⁹ [REDACTED]

²⁰ Complete physical examination at Visit 20, Visit 160 and Visit 1999 (EOS) in Part 1 and Visit 2999 (EOS) in Part 2. Abbreviated physical examinations will be performed at the other visits.

²¹. Hematology analysis includes red blood cell count (RBC), white blood cell count (WBC), platelet counts, hematocrit, hemoglobin, reticulocytes, neutrophils, etc.

X = assessment to be recorded in clinical database

S = assessment to be recorded in source documentation only

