9.1 Adverse events

An AE is any untoward medical occurrence (i.e., any unfavorable and unintended sign [including abnormal laboratory findings], symptom or disease) in a subject after providing written informed consent for participation in the study until the end of study visit. Therefore, an AE may or may not be temporally or causally associated with the use of a medicinal (investigational) product.

In addition, all reports of intentional misuse and abuse of the study treatment are also considered an adverse event irrespective if a clinical event has occurred. See [Section 9.5](#) for an overview of the reporting requirements.

The occurrence of AEs must be sought by non-directive questioning of the subject at each visit during the study. Adverse events also may be detected when they are volunteered by the subject during or between visits or through physical examination finding, laboratory test finding, or other assessments.

Abnormal laboratory values or test results constitute adverse events only if they fulfill at least one of the following criteria:

- they induce clinical signs or symptoms,
- they are considered clinically significant,
- they require therapy.

Clinically significant abnormal laboratory values or test results should be identified through a review of values outside of normal ranges/clinically notable ranges, significant changes from baseline or the previous visit, or values which are considered to be non-typical in patients with underlying disease. Investigators have the responsibility for managing the safety of individual subject and identifying adverse events. Alert ranges for liver events are included in [Appendix 1](#).

Adverse events should be recorded on the appropriate CRF capturing AEs under the signs, symptoms or diagnosis associated with them, and accompanied by the following information:

1. The severity grade
 - mild: usually transient in nature and generally not interfering with normal activities
 - moderate: sufficiently discomforting to interfere with normal activities
 - severe: prevents normal activities
2. its relationship to the study treatment
3. its duration (start and end dates) or if the event is ongoing an outcome of not recovered/not resolved must be reported.
4. whether it constitutes a SAE (see [Section 9.2](#) for definition of SAE) and which seriousness criteria have been met
5. Action taken regarding investigational treatment.

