All adverse events must be treated appropriately. Treatment may include one or more of the following

 - no action taken (e.g. further observation only)
 - investigational treatment dosage increased/reduced
 - investigational treatment interrupted/withdrawn
 - concomitant medication or non-drug therapy given
 - hospitalization/prolonged hospitalization (see [Section 9.2](#) for definition of SAE)
6. its outcome (not recovered/not resolved; recovered/resolved; recovered/resolved with sequelae; fatal; or unknown)

Information about common side effects already known about the investigational drug can be found in the IB or will be communicated between IB updates in the form of Investigator Notifications. Once an adverse event is detected, it must be followed until its resolution or until it is judged to be permanent, and assessment should be made at each visit (or more frequently, if necessary) of any changes in severity, the suspected relationship to the investigational drug, the interventions required to treat it, and the outcome.

The investigator must also instruct each subject to report any new adverse event (beyond the protocol observation period) that the subject, or the subject's personal physician, believes might reasonably be related to study treatment. This information must be recorded in the investigator's source documents; however, if the AE meets the criteria of an SAE, it must be reported to Novartis.

Refer to the Site Operations Manual for data capture methodology regarding AE collection for subjects that fail screening.

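### Protocol 7.2 gives the EOS label to a visit within 14 days of an early treatment stop, although EOS is otherwise about 90 days after last dose and AE collection ends at EOS

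*Protocol*

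**What the plan says.** Four parts of the protocol bear on this.

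- **7.2 (early stop).** Patients who stop treatment are not counted as withdrawn unless they withdraw consent. Where possible, "they should return for EOS visit within 14 days after last study medication administration".
- **3.1 and 8.1 footnote 15 (timing of EOS).** Section 3.1 has patients return "approximately 90 days after last dosing for study completion evaluations (EOS"). The footnote gives Day 90 as end of treatment and Day 180 as EOS in Part 1. For Part 2, "Day 180 (Visit 180) is End of Treatment (EOT) and Day 270 (Visit 2999) is End of Study (EOS").
- **7.1 (90-day visit).** Everyone who was randomized or took study drug "should have a safety follow-up visit 90 days after last administration of study treatment. The information collected is kept as source documentation". The section does not call this visit EOS, and SAEs are the only events for which it sets a reporting duty.
- **9.1 (AE window).** An AE is an untoward occurrence "after providing written informed consent for participation in the study until the end of study visit". Subjects are also told "to report any new adverse event (beyond the protocol observation period") if they or their physician think it may be related to study drug. Such an event goes into the source documents, and "if the AE meets the criteria of an SAE, it must be reported to Novartis".

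Protocol 9.2.2 runs SAE reporting to 90 days after last dose, without reference to EOS. SAP 8.2 counts AEs as treatment-emergent up to 7 days after discontinuation, and summarizes post-treatment AEs and SAEs separately for SAF1 and SAF2.

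**The concern.** The EOS label fixes a data boundary, because 9.1 uses it to close the AE window. If a site takes 7.2 at its word, a patient who stops drug but stays in the study reaches EOS within two weeks, and the window for new non-serious AEs closes then. A patient who completes treatment is covered for about 90 days after last dose.

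Both kinds of patient enter the same post-treatment AE tables, so early stoppers could contribute a shorter collection period than completers. Early stoppers are also not a random subset: the reasons listed in 7.2 include safety concerns, laboratory abnormalities and COVID-19. Sites could resolve the conflict differently, and the tables would not show which reading each site had used.

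**Working it through.** Only day counts are needed.

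**1. Reproduce the stated interval.** EOS minus end of treatment, from footnote 15:
- Part 1: 180 − 90 = 90 days.
- Part 2: 270 − 180 = 90 days.

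Both agree with the 90 days or so in 3.1. The footnote gives fixed study days, so it matches a count from last dose only for patients who complete treatment.

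**2. Literal reading of 7.2 with 9.1.** Let v be the day of the early visit after last dose, with v ≤ 14. The AE window closes at v instead of 90, so the gap is 90 − v.
- v = 14: 90 − 14 = 76 days.
- v = 7: 90 − 7 = 83 days.

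Fourteen days is a maximum, so 76 days is the smallest gap on this reading.

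**3. Alternative reading.** If the site treats the 90-day visit in 7.1 as EOS, the gap is 90 − 90 = 0 days.

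**4. Which outputs are exposed.**

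| Output | Window | Exposed on the literal reading? |
|---|---|---|
| SAE reporting (Protocol 9.2.2) | 90 days after last dose | No; not tied to EOS |
| Primary analysis (Protocol 11.4.3) | Data up to treatment discontinuation | No |
| Treatment-emergent AEs (SAP 8.2) | 7 days after discontinuation | Only if v < 7; then 7 − v days |
| Post-treatment AE summaries (SAP 8.2) | Later events, SAF1 and SAF2 | Yes, for new non-serious AEs |

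**5. How many patients.** The documents do not say. The nearest figure is in Protocol 11.7: 48 enrolled in Part 1 so that at least 40 complete, which allows for 48 − 40 = 8 drop-outs. That is a planning allowance, and it includes consent withdrawals, to whom the point does not apply because 7.3 ends their assessments.

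**The case against.** The strongest reply is that the rest of the protocol assumes follow-up goes on. Section 7.1 asks for a 90-day visit for everyone randomized or treated. Section 7.4 does not let a patient be declared lost until the scheduled EOS visit would have occurred. Section 9.2.1 says that serious and non-serious AEs alike are captured on the CRF. The sentence in 7.2 applies only where possible, and it also covers people who no longer wish to take part, for whom a prompt last visit is sensible and agrees with 8.1. Visit detail is left to a Site Operations Manual that is not available here.

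Much of this stands, and it rules out three stronger readings that a reader might infer.

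- **That sites are released from recording later AEs.** They are not. AEs believed related must still go into source documents, and AEs already detected are followed to resolution. What is left open is CRF entry of new non-serious events.
- **That 90-day data stay out of the database.** Section 7.1 says the information is kept as source documentation; it does not say only there. The schedule has a separate S code for items held in source documentation only, while its final-visit columns carry items under the key "X = assessment to be recorded in clinical database". Section 7.1 applies to completers too, so a source-only reading would contradict the schedule for everyone.
- **That a number of off-treatment visits is lost, with damage to the first-morning-void UPCR analysis to EOS.** The documents set out no follow-up schedule for early stoppers, so there is no count to subtract from.

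The reply does not remove the conflict itself. Section 7.1 never calls its visit EOS. The CRF statement in 9.2.1 depends on an AE definition that stops at EOS. The provision in 8.1 is for subjects who leave the study, whereas 7.2 says that stopping drug is not withdrawal. Section 7.4 refers to a scheduled EOS date, which is the date in dispute.

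**Conclusion.** The protocol contradicts itself on when EOS falls for patients who stop drug but stay in the study, and through 9.1 this leaves their AE window unclear. The stretch in which new non-serious AEs need not be entered on the CRF is 0 days or at least 76 days, depending on how a site reads the text. The larger figure assumes that the early visit takes place and is treated as the visit that closes AE collection.

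The consequence is confined to the post-treatment AE summaries for SAF1 and SAF2. The treatment-emergent tables are affected only when the early visit is held before day 7. The number of patients is not given and is probably small. This is a minor inconsistency of wording. It does not threaten the efficacy conclusions or the capture of serious events.

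**What to change.** - **7.2:** call the visit within 14 days an early end-of-treatment visit.
- **7.1:** state that the 90-day safety follow-up visit is the EOS visit, and that CRF collection of all AEs, serious or not, continues until that visit for every treated patient who has not withdrawn consent.

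Because footnote 15 uses fixed study days, a clause saying that those days apply to patients who complete treatment, and that EOS is otherwise counted from last dose, would prevent a new mismatch.

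The cost is a short wording change through the written amendment that 13.1 requires. It adds no visit, since 7.1 already asks for the one at 90 days, and it needs no change to the SAP.

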7.3 Withdrawal of informed consent

Subjects may voluntarily withdraw consent to participate in the study for any reason at any time. Withdrawal of consent occurs only when a subject:

- Does not want to participate in the study anymore, and
- Does not allow further collection of personal data

In this situation, the investigator should make a reasonable effort (e.g. telephone, e-mail, letter) to understand the primary reason for the subject's decision to withdraw his/her consent and record this information.

Study treatment must be discontinued and no further assessments conducted, and the data that would have been collected at subsequent visits will be considered missing.

Further attempts to contact the subject are not allowed unless safety findings require communicating or follow-up.

All efforts should be made to complete the assessments prior to study withdrawal. A final evaluation at the time of the subject's study withdrawal should be made as detailed in the assessment table.

Novartis will continue to keep and use collected study information (including any data resulting from the analysis of a subject's samples until their time of withdrawal) according to applicable law.

For US and Japan: All biological samples not yet analyzed at the time of withdrawal may still be used for further testing/analysis in accordance with the terms of this protocol and of the informed consent form.

For EU and RoW: All biological samples not yet analyzed at the time of withdrawal will no longer be used, unless permitted by applicable law. They will be stored according to applicable legal requirements.

7.4 Lost to follow-up

For subjects whose status is unclear because they fail to appear for study visits without stating an intention to discontinue or withdraw, the investigator should show "due diligence" by documenting in the source documents steps taken to contact the subject, e.g. dates of telephone calls, registered letters, etc. A subject cannot be formally considered lost to follow-up until his/her scheduled end of study visit would have occurred.

7.5 Study Stopping rules

The DMC will perform safety reviews of blinded data throughout the study. The first blinded data safety review will occur one month after the first dose of study drug and then monthly thereafter. If the DMC decides that an un-blinded safety data review is necessary, a copy of the randomization list will be requested from (and provided by) the Independent Programmer and Independent Statistician. The DMC charter provides complete details of this process.

In addition, DMC will conduct ad hoc safety evaluation in a timely manner and provide its recommendation on study conduct should the circumstance below arise:

- One fatal or life-threatening SAE occurs, that is considered by the Investigator as potentially or possibly related to LNP023.
- The Sponsor or DMC considers that the number and/or severity of AEs, abnormal safety monitoring tests or abnormal laboratory findings justify an ad hoc safety evaluation.

If a full safety review is triggered, the DMC will be asked to perform a review of the safety data in an unblinded manner (SAEs and other safety information as necessary), the DMC can recommend (i) for the study to continue without amendment, (ii) to continue the study with modifications to the protocol (iii) to stop the study.

